### 6.2.3 Definition of Maximum Tolerated Dose (MTD)

The MTD was defined as the highest dose of taselisib tested in which a DLT is experienced by 0-1 out of 6 patients among the dose levels. The dose of enzalutamide remained constant. The first cohort of patients (3 patients) in each arm started at dose level 1, and each patient was observed for 4 weeks on the specified dose and instructions were followed as below:

- If no patient in the first cohort of 3 experiences a DLT, dose escalation will proceed and patients will be accrued at the next dose level. If 1 of these patients experiences a DLT, the cohort will be expanded to 6 patients. If <33% of these patients experiences a DLT (e.g., 1 of 6 patients), dose escalation may proceed.
- If a DLT is observed in  $\geq 33\%$  of the patients in a given cohort (e.g.  $\geq 2$  of 6 patients), the MTD will have been exceeded and the lower dose level will be evaluated.

An exception to the above rule would be in the case in which the two DLTs observed out of 6 patients are both hematologic in nature and potentially reflect poor bone marrow reserve in this heterogeneous patient population and not the true MTD for the combination. In this instance, up to 3 additional patients may be enrolled to expand the total cohort size to 9 patients to assess for further DLT. In this situation, if a third DLT is observed, the MTD will have been exceeded and the lower dose level will be evaluated.

- If the 2 mg dose does not exceed the MTD, then dose escalation will proceed to the 4 mg dose. If the 4 mg dose does not exceed the MTD, then dose escalation will proceed to the 6 mg dose, and if the 6 mg dose does not exceed the MTD, then dose escalation will proceed to the 8 mg dose. If <33% of patients experience a DLT in the 8 mg cohort, then this dose level will be the maximum administered dose (MAD).

No new cohort of patients will be treated until the previous cohort has been fully evaluated for toxicity. Patients requiring dose reduction for reasons other than a DLT in cycle 1 of the phase Ib portion will not be included in the DLT evaluation. If the frequency of Grade 3 or 4 toxicities or other unacceptable lower grade chronic toxicities in the phase 1b portion suggests that the MTD has been exceeded at that dose level, any remaining accrual at that dose level will be halted and a lower dose of taselisib may be examined.

If taselisib dosing is not well tolerated, a less frequent dosing schedule may be evaluated at the same or lower dose of taselisib in that arm. Consistent with the dose escalation rules above, the lowest dose level will be 2 mg, and the highest dose level will be 8 mg.

## 6.3 Phase II component of the trial

Based on the phase Ib and data from other studies of taselisib, the recommended dose of taselisib for phase II is 4 mg. Note that dose reduction within patients (individually) is allowed. Dose reduction will be required for a given patient in case of grade 3 or 4 toxicities.

The primary efficacy endpoint is clinical benefit rate (CBR) of enzalutamide + taselisib in patients with androgen receptor positive triple negative metastatic breast cancer. Secondary objectives are to determine the ORR and progression free survival (PFS). CBR is defined as the proportion of patients achieving a complete response (CR) plus partial response (PR) plus stable disease (SD)

for at least 16 weeks. To assess objective responses, we will estimate the overall tumor burden at baseline to which subsequent measurements [performed every 2 cycles using the Solid Tumor Response Criteria (RECIST) v1.1] will be compared.

Section 6.3.1 and 6.3.2 discuss administration of taselisib and enzalutamide. Patients on the combination arm can take both drugs at the same time. Patients on the enzalutamide only arm should take enzalutamide only as directed below.

### 6.3.1 Taselisib

Taselisib tablets are administered once daily until disease progression or intolerable toxicity. Taselisib administration will begin on C2D1 for patients enrolled on the combination arm (with enzalutamide alone beginning on C1D1). Each dose should be taken with a minimum of 3–4 ounces (90–120 mL) of water with or without food in the morning (before noon). If a dose is missed (not taken by noon), the patient will resume dosing with the next scheduled dose. Missed or vomited doses will not be made up. The occurrence and frequency of any vomiting during a treatment cycle must be noted as an adverse event. Patients should swallow the capsules as a whole and not chew or crush them.

A sufficient number of taselisib tablets should be provided to the patient to last until the next cycle. Patients will be instructed to bring their bottles of study drug and their medication diary with them to each study visit.

### 6.3.2 Enzalutamide

The daily dose of enzalutamide is 160 mg/day given in 4 capsules (40 mg each) by mouth. Enzalutamide capsules are administered once daily until disease progression or intolerable toxicity. The first ten subjects on the enzalutamide + taselisib arm at Vanderbilt will have blood draws for PKs as outlined in the study calendar.

Patients should be instructed to take the dose of enzalutamide at the same time in the morning (before noon) every day, with or without food. Enzalutamide should be taken with a glass of water. Patients should swallow the capsules as a whole and not chew, crush, or open them.

If the patient forgets to take her/his dose and it is past noon, then the dose should be withheld that day and enzalutamide should be restarted the following day. Missed or vomited doses will not be made up. The occurrence and frequency of any vomiting during a treatment cycle must be noted as an adverse event.

A sufficient number of enzalutamide capsules should be provided to the patient to last until the next visit or, at the investigator's discretion, to last until the next cycle. Patients will be instructed to bring their bottles of study drug and their medication diary with them to each study visit.

## 6.4 Concomitant Treatment and Supportive Care Guidelines

### 6.4.1 Concomitant Therapy and Drug-drug Interactions

Concomitant therapy includes any prescription medications or over-the-counter preparations used by a patient between the 7 days preceding day 1 of treatment and the treatment completion visit.

All concomitant medications should be documented. Patients who experience toxicities may be treated symptomatically as clinically indicated. Patients treated with anti-convulsant medications (see below for restrictions) should have levels monitored regularly.

Enzalutamide is a strong inducer of CYP3A4 and a moderate inducer of CYP2C9 and CYP2C19. Taselisib is a substrate of CYP3A4, and results of a clinical study with a potent CYP3A4 inhibitor (itraconazole) suggest that there is a moderate potential for a drug-drug interaction between taselisib and any medication that strongly inhibits CYP3A4. Therefore, the concomitant use of strong CYP3A4 inhibitors should be avoided. The effects of strong/moderate CYP3A4 inducers on the pharmacokinetics of enzalutamide have not been evaluated in vivo. Co-administration of enzalutamide may decrease the plasma exposure of enzalutamide and should be avoided. If use of one of these drugs is necessary, the risks and benefits should be discussed with the Protocol Chair and documented prior to its concomitant use with taselisib and enzalutamide:

- Strong/moderate CYP3A4 inhibitors or inducers (which should be avoided): atazanavir, bosentan, carbamazepine, ciprofloxacin, clarithromycin, cyclosporine, efavirenz, erythromycin, etravirine, fluconazole, hyperforin (St. Johns Wort), indinavir, itraconazole, ketoconazole, modafinil, nafcillin, nefazodone, nelfinavir, oxcarbazepine, phenobarbital, phenytoin, posaconazole, quinidine, rifabutin, rifampin, rifapentine, ritonavir, saquinavir, sirolimus, tacrolimus, telithromycin, troleandomycin, verapamil, and voriconazole.
- CYP2C8 inhibitors or inducers: gemfibrozol should be avoided.
- Strong P-glycoprotein inhibitors, including cyclosporine, amiodarone and quinidine should be avoided
- *In-vitro* protein binding studies have shown that enzalutamide can displace coumarin anticoagulants from binding sites. Patients already on coumarin anticoagulants should have closely monitored Prothrombin times while taking enzalutamide.
- Grapefruit juice or grapefruit supplements should be avoided.

See the following websites for updated lists of CYP inhibitors, inducers, and substrates:

- <http://www.fda.gov/Drugs/DevelopmentApprovalProcess/DevelopmentResources/DrugInteractionsLabeling/ucm093664.htm#potency>
- [REDACTED]

#### 6.4.2 Excluded Therapy

Use of the following therapies is prohibited for  $\leq 14$  days prior to Cycle 1 Day 1 dosing and during the study.

- Any experimental concomitant therapy intended for the treatment of cancer, including chemotherapy, radiotherapy, immunotherapy, biologic therapy, herbal therapy, or hormonal therapy. Bisphosphonate and denosumab therapy for bone metastases is allowed.
- Quinidine or other anti-arrhythmic agents are prohibited

#### 6.5 Assessments during Treatment

All visits must occur within  $\pm 3$  days from the scheduled date, unless otherwise noted. Please see the Study Calendar at the beginning of this protocol for the schedule of treatment period assessments.

## 6.6 Cross-over post-progression

Patients who are randomized to enzalutamide alone can crossover to receive enzalutamide + taselisib upon disease progression. Patients who are randomized to enzalutamide alone and who discontinue enzalutamide for toxicity cannot crossover to receive single agent taselisib. However, patients on the enzalutamide + taselisib arm can continue to receive single agent taselisib if they discontinue enzalutamide due to toxicity. Patients who cross over to receive taselisib in combination with enzalutamide will follow the assessments and procedures as outlined in the study calendar. The duration of each cycle will continue to be 28 days and the cycle numbers will "reset" to 1 and will be followed by the "X" suffix (e.g., Cycles 1X, 2X, etc.). Crossover therapy (taselisib) must begin no later than 21 days after the clinic visit at which progression is determined, but can begin as early as C1XD1.

Patients must have labs and procedures performed as outlined in the cross-over study calendar and must meet the values as described in the Inclusion Criteria, prior to receiving taselisib based on assessments and procedures performed within 28 days prior to Day 1 of Cycle 1X. Labs and procedures not included in the cross-over study calendar do not have to be repeated. Patients must also agree to a tumor biopsy, as outlined in the eligibility criteria, prior to initiating taselisib. Patients will receive crossover treatment until progression, intolerable toxicity, or elective withdrawal from the study. Patients who crossover will be evaluated with radiologic assessments every 2 cycles until disease progression.

## 6.7 Duration of Therapy

Duration of therapy will depend on individual response, evidence of disease progression and tolerance. In the absence of treatment delays due to adverse events, treatment may continue until one of criteria in Section 6.9 applies.

## 6.8 Duration of Follow-Up

Participants will be followed for 30 days after the final dose of study drug. The 30 day follow-up can be done by phone or through a clinic visit. Patients who at the treatment completion visit have an ongoing serious adverse event or an adverse event leading to treatment discontinuation will be followed every 3 months until the event resolves, the investigator assesses the event as stable, or the patient is lost to follow-up. Participants will also be followed annually for disease progression by phone, and if necessary, by chart review. If the patient is no longer coming to the institution for care, then the patient may be called as needed for follow-up.

## 6.9 Criteria for Removal from Study

Patients will be removed from study when any of the criteria listed below apply. All patients who initiate protocol treatment will be included in the overall evaluation of response (intent-to-treat analysis). All reasons for discontinuation of therapy should be documented clearly in the medical record.

If a subject discontinues or withdraws from the study, every attempt will be made to get a tissue/tumor biopsy at the end of treatment, along with blood if the subject is able and willing to do so.

Patients may be withdrawn from the study if they experience any of the following:

- Disease progression, per investigator assessment
- Intolerable toxicity to taselisib or enzalutamide. Patients experiencing toxicity to taselisib or enzalutamide can continue on study with single agent enzalutamide or taselisib, respectively, at the discretion of the treating physician. Patients will be followed for disease progression and should continue radiologic assessments every 2 cycles as per the study.

Other reasons for patient discontinuation may include, but are not limited to, the following:

- Non-compliance with the study protocol, including, but not limited to not attending the majority of scheduled visits. The Protocol Chair will determine when non-compliance should lead to removal from study. Note: The patients will still be included in the overall evaluation of response (intent-to-treat analysis).
- Patient personal decision. The reason for discontinuation from the study must be documented. The patients will be included in the overall evaluation of response (intent-to-treat analysis) if any protocol therapy was administered prior to withdrawal.
- If the patient becomes pregnant
- Patient is lost to follow-up
- Study is terminated for any reason

The investigator has the right to discontinue a patient from the study for any medical condition that the investigator determines may jeopardize the patient’s safety if he or she continues in the study; for reasons of noncompliance (e.g., missed doses, visits); or if the investigator determines it is in the best interest of the patient. The Protocol Chair should be notified in such cases.

## 7. EXPECTED TOXICITIES AND DOSING DELAYS/DOSE MODIFICATIONS

### 7.1 Dose Modifications/ Delays

Table 2 below lists dose level reductions for taselisib and enzalutamide. Please see section 7.2 to 7.4 for thresholds to reduce doses.

Table 2: Dose Modifications			
Taselisib dose level reductions			
Starting dose	First reduction	Second reduction	
4 mg daily	2 mg daily	Discontinue	
Enzalutamide dose level reductions			
Starting dose	First reduction	Second reduction	Third reduction
160 mg daily	120 mg daily	80 mg daily	Discontinue

## 7.2 Taselisib

See Table 3 at the end of this section for taselisib dose modification criteria

Patients who experience an SAE or whose treatment is interrupted or permanently discontinued due to an adverse event or clinically significant laboratory value must be followed as outlined in Table 3 below, at least once a week for 4 weeks, and subsequently at 4-week intervals, until resolution or stabilization of the event, whichever comes first. If a patient requires a dose delay of > 28 days from the intended day of the next scheduled dose, then the patient should be discontinued from the study. All patients must be followed for adverse events and serious adverse events for 30 days following the last dose of taselisib. This can be done as either an in-office visit or by phone. If the taselisib dose is reduced due to an adverse event which is later determined to be secondary to enzalutamide and enzalutamide is discontinued, taselisib can be re-escalated at the discretion of the treating physician after consultation with the Protocol Chair. If both taselisib and enzalutamide are held for an adverse event, enzalutamide should be restarted at the original dose. Taselisib should be restarted at one dose lower than the last dose. After 28 days, if the patient is tolerating both medications well, taselisib may be increased back to the original dose.

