Grade 3	
First Occurrence:
 
 
• Hold taselisib and initially manage with antidiarrheals.
 
• Obtain stool culture for infectious workup.
 
• For Grade 3 diarrhea or colitis, treat with systemic corticosteroids (prednisone 60-80 mg QD equivalent or solumedrol 16-20 mg IV q 8 h to start). Can increase steroid dosage if diarrhea does not improve.
 
• Concurrent infections (e.g., Clostridium difficile, enteric bacteria, CMV) should be treated with the appropriate antibiotic.
 
• For patients that do not improve upon 48 hours of corticosteroid treatment, a colonoscopy is recommended to evaluate for other causes of diarrhea (e.g. CMV colitis)
 
 
If diarrhea or colitis improves to Grade <math>\leq</math>1 and upon completion of any steroid taper or antibiotic treatment, resume taselisib treatment at one dose level lower.
 
Second Occurrence:
 
 
• Discontinue taselisib
 

Grade 4	
 
• Discontinue taselisib.
 

Rash	

Special considerations	
 
Permanently discontinue for any rash with concurrent signs/symptoms strongly suggestive of a severe Type 1 hypersensitivity or anaphylactic/anaphylactoid reaction, fever, or with painful desquamation or mucosal involvement suggestive of Stevens-Johnson Syndrome/ toxic epidermal necrolysis, or with other life-threatening complications
 

Grade 1	
 
Continue dosing at current dose and monitor for change in severity (consider contacting patient between study visits). Consider prescribing topical steroidsc.
 

Grade 2	
 
Monitor closely for change in severity and hypersensitivity-related systemic symptoms (contact patient weekly between study visits)
 
Consider prescribing topical steroidsc
 
Consider dermatological consultation
 
Consider one or more of the following:               
 
Hold dose until resolution to <math>\leq</math> Grade 1, then resume at next lower dose level
 
Dose reduction
 
Initiation of oral steroid treatment unless contraindicatedd, monitor blood sugar carefully if initiating steroids while continuing taselisib
 
 
 

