### 7.3.2 Other toxicities

Asthenia/fatigue, back pain, diarrhea, arthralgia, hot flush, peripheral edema, musculoskeletal pain, headache, upper respiratory infection, muscular weakness, dizziness, insomnia, lower respiratory infection, spinal cord compression and cauda equina syndrome, hematuria, paresthesia, anxiety, and hypertension have all occurred on studies of enzalutamide.

Though not expected, if  $\geq$  grade 3 diarrhea occurs that is not controlled with anti-diarrheal agents (e.g. loperamide), enzalutamide should be withheld until resolution to  $\leq$  grade 1, then reinstated at the next lower dose level.

If toxicities are  $\leq$  grade 2, manage symptomatically if possible and retreat without dose reduction.

If toxicities are  $\geq$  grade 3, except for anemia, treatment should be withheld until resolution to  $\leq$  grade 1 or baseline if baseline was greater than grade 1, then reinstated, if medically appropriate, at the next lower dose level.

For any grade 3 or 4 toxicity not mentioned above, treatment should be withheld until the patient recovers completely or to grade 1 toxicity. The treatment should then be resumed at the next dose level. For grade 1 or 2 toxicities, no dose reduction should be made.

A maximum of two weeks will be permitted for resolution of grade 3 or 4 toxicities. If toxicity has not resolved by the end of two weeks, patient will be taken off study.

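### When both drugs are held, mainly for a first grade 3 event other than anemia, 7.2 restarts enzalutamide at the original dose and 7.3.2 one level lower (160 v 120 mg), and nothing says which governs

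*Combined protocol and SAP*

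**What the plan says.** **Section 7.2 (taselisib).** For a double hold: "If both taselisib and enzalutamide are held for an adverse event, enzalutamide should be restarted at the original dose". The next sentence reads: "Taselisib should be restarted at one dose lower than the last dose". Taselisib may go back to its original dose after 28 days if the patient tolerates both drugs. The sentence before the restart rule deals with a taselisib reduction made for "an adverse event which is later determined to be secondary to enzalutamide" when enzalutamide has been discontinued, so this paragraph has events caused by enzalutamide in view. The restart sentence itself mentions neither grade nor cause.

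**Section 7.3.2 (enzalutamide).** After toxicity of grade 3 or more, anemia excepted, treatment is withheld until recovery, "then reinstated, if medically appropriate, at the next lower dose level". Diarrhea has its own sentence: "grade 3 diarrhea occurs that is not controlled with anti-diarrheal agents (e.g. loperamide), enzalutamide should be withheld until resolution to" grade 1 or below, "then reinstated at the next lower dose level", here without the words on medical appropriateness. Neither sentence makes an exception for a patient whose taselisib is also on hold. Hot flashes follow a separate, discretionary rule in 7.3.1.

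**Section 7.1, Table 2.** Under "Enzalutamide dose level reductions" the steps are 160, 120 and 80 mg, then discontinuation. Taselisib goes from 4 to 2 mg and then stops. The text above the table sends the reader to 7.2 through 7.4 together and ranks none of them.

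**The concern.** A site that has stopped both drugs for the same grade 3 event can find two instructions for enzalutamide and follow either one correctly. In a multi-institution trial, like patients may then be re-treated at different doses.

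The safety side matters more. If enzalutamide is the suspected cause, the 7.2 default brings the suspected drug back at full dose and takes the reduction from the other drug. Section 7.3.2 is there to reduce enzalutamide in that case.

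**Working it through.** No error rate or sample size is involved. The check is to apply both rules to the same patient.

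**Step 1: does the protocol's own text produce a double hold?** Take a first grade 3 diarrhea in a patient on 160 mg enzalutamide and 4 mg taselisib.
- Table 3, Diarrhea, Grade 3, first occurrence: "Hold taselisib and initially manage with antidiarrheals". Taselisib is now held.
- If anti-diarrheals do not control it, the diarrhea sentence of 7.3.2 withholds enzalutamide. Both drugs are now held.

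**Step 2: restart doses under each rule.**

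| | Enzalutamide | Taselisib |
|---|---|---|
| 7.2, double hold | 160 mg | 2 mg, may return to 4 mg after 28 days if both are tolerated |
| 7.3.2 for enzalutamide, Table 3 for taselisib | 120 mg | 2 mg |

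- Enzalutamide: 160 − 120 = 40 mg/day; 40/160 = 25%. With 40 mg capsules (6.3.2), 160/40 = 4 capsules v 120/40 = 3.
- Taselisib: 4 − 2 = 2 mg; 2/4 = 50%, the same first step under both rules in this example. Only the enzalutamide dose differs.

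**Step 3: which grades reach the conflict?** The 7.2 sequence supposes that taselisib restarts. For taselisib-related grade 4 diarrhea, rash, hematologic toxicity, pneumonitis and other clinically significant toxicity, Table 3 stops taselisib permanently; hyperglycemia is the exception. A second grade 3 diarrhea and a rash with fever also end taselisib. That leaves mainly the first grade 3 event.

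**Step 4: does any other text settle it?**
- 7.1 names 7.2 to 7.4 without an order of precedence.
- 7.4 lets the investigator reduce a dose for toxicity of any grade, and asks that changes to the guidelines go to the Protocol Chair beforehand. It does not say which restart dose is the guideline and which is the change.
- 6.3 requires a dose reduction after grade 3 or 4 toxicity but does not name the drug. The 7.2 sequence meets it through taselisib and the 7.3.2 sequence through enzalutamide.

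**Step 5: a patient already reduced to 120 mg.** Section 7.3.2 gives 80 mg. Section 7.2 gives 160 mg if the original dose means the starting dose, or 120 mg if it means the dose before the hold. The text does not define it.

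**The case against.** The best reply is that the specific rule governs the general one. The 7.2 sentence is the only general restart rule written for both drugs held together. Section 7.3.2 must also serve the enzalutamide-only arm, where no double hold can occur. The headings point the same way: Table 3 is for taselisib-related toxicity, and 7.3 is the enzalutamide section. This is a reasonable reading, and a site could adopt it.

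It does not cure the problem. No sentence states that order or that split by cause. The disputed sentence, although placed under taselisib, is an instruction on enzalutamide dose. If 7.2 does govern every double hold, full-dose enzalutamide with a taselisib cut becomes the default even when enzalutamide is the suspected cause.

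A second reply is that the diarrhea case is constructed. No Table 3 row tells sites to hold enzalutamide, the explicit instructions to hold both drugs belong to the completed phase Ib, and 7.3.2 itself calls such diarrhea unexpected. That is fair as to frequency. But 7.2 writes a rule for the double hold, so the protocol expects it to occur.

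A third reply is that the words on medical appropriateness in 7.3.2 leave room. They bear most naturally on whether to reinstate rather than on the dose level, and the diarrhea sentence lacks them.

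**Conclusion.** The two sections conflict for patients taking both drugs, mainly after a first grade 3 event other than anemia. From the starting dose the difference is one enzalutamide level, 160 v 120 mg. It is a defect in a dosing and safety instruction. Design, sample size and the primary analysis are unaffected, and any effect on the clinical benefit rate cannot be computed and is likely small.

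A reader might infer more than the documents support:
- **That every event of grade 3 or more is affected.** Most taselisib-related grade 4 events end taselisib, so the 7.2 restart sequence does not arise.
- **That a full-dose restart is compelled.** Section 7.4 allows a reduction at any grade.
- **That taselisib is halved for good.** Section 7.2 allows a return to the original dose after 28 days.
- **That double holds are common.** The diarrhea rates in 3.3.1.1 come from other regimens, mostly at taselisib doses above 4 mg, and count taselisib-related events rather than holds of both drugs. The rash with fever in 7 of 8 combination patients (7.2.1.3) does not show it either: Table 3 now ends taselisib for rash with fever, and the enzalutamide lead-in was added in response. The documents give no frequency.

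**What to change.** In 7.2, limit the restart at the original dose to events not attributed to enzalutamide, and state that when enzalutamide is a suspected cause the 7.3.2 / Table 2 reduction (160 to 120 to 80 mg) applies. The same edit can say whether the original dose means the starting dose or the dose before the hold.

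In 7.3.2, add a matching cross-reference to the diarrhea sentence and to the sentence on grade 3 or more: when both drugs are held and the event is not attributed to enzalutamide, follow 7.2.

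Dosing by attribution is a policy choice for the sponsor. If the sponsor prefers one rule for every double hold, the minimum is a single sentence naming the section that governs. If that section is 7.2, the text should make clear that full-dose enzalutamide is intended even when enzalutamide is suspected.

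The cost is a few sentences in a protocol amendment, with the ethics approval at each institution that 14.1 requires. Nothing changes in design, sample size or data collection.
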